3.2.3 DEFINITION OF RESPONDER AND NON-RESPONDER

Table 5: Definition of Secondary Regression Endpoint Responder and Non-Responder

Responder	Non-Responder
Subject with no histologic evidence of cervical HSIL ^a at Week 36 visit ^b AND Subject in whom an excision or biopsy sample ^c was NOT obtained between initial dose up to Week 36 visit	Subject with histologic evidence of cervical HSIL, AIS, cervical carcinoma at Week 36 visit OR Subject in whom an excision or biopsy sample was obtained between initial dose up to Week 36 visit OR Subjects with no Week 36 visit sample result

^a No evidence of HSIL is defined by histology as negative, squamous atypia, or LSIL

^b The efficacy time frame is defined by those who have undergone a biopsy or surgical excision at any time starting from 14 days prior to the protocol-specified target date of Week 36. The first tissue r_moval sample determines the histology endpoint. ^c Excludes ECC-only samples

Table 6: Definition of Secondary Complete Regression Endpoint Responder and Non-Responder

Responder	Non-Responder
Subject with no histologic evidence of cervical HSIL squamous atypia, or LSIL at Week 36 visit ^a AND Subject in whom an excision or biopsy sample ^b wa NOT obtained between initial dose up to We k 36 visit	 Subje t with histologic evidence of cervical HSIL, squamous atypia, LSIL, AIS, cervical or carcinoma at Week 36 visit OR Subject in whom an excision or biopsy sample was obtained between initial dose up to Week 36 visit OR Subjects with no Week 36 visit sample result

^a The efficacy time frame is defined b those who have undergone a biopsy or surgical excision at any time starting from 14 days prior to the protocol-specified target **date of Week 36**. The first tissue removal sample determines the histology endpoint. ^b Excludes ECC-only samples.

Table 7: Definition of Secondary Non-progression Endpoint Responder and Non-Responder

Responder	Non-Responder
Subject with no histologic evidence of a worsening	Subject with histologic evidence of worsening of cervical
of cervical condition at Week 36 visit ^a relative to	condition at Week 36 visit relative to baseline
baseline	OR
AND	Subject in whom an excision or biopsy sample was obtained
Subject in whom an excision or biopsy sample ^b was	between initial dose up to Week 36 visit
NOT obtained between initial dose up to Week 36	OR
visit	Subjects with no Week 36 visit sample result

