6.4.14 ECTOCERVICAL BIOPSIES

Ectocervical biopsies are requiled at Screening to confirm eligibility.

Biopsies should not be performed at any other visit unless there is suspicion of disease progression. Removal of additional tissue by biopsy before Week 36 will bias results toward improvement regardless of whether the subject is in the active or placebo group. For this reason, if biopsies are obtained prior to the Week 36 visit, the subject will be classified as a non-regressor in the efficacy analyses. Subject safety is paramount in this study. Therefore, if at any time the investigator may suspect disease progression and the standard of medical care would be to perform an unscheduled biopsy prior to Week 36, then his or her medical judgment should prevail over the default "Schedule of Events", Table 1.

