6.4.15 UNSCHEDULED BIOPSIES

In the event an unscheduled biopsy is performed prior to the Week 36 visit, the subject will be classified as a non-responder in the efficacy analyses. The subject may discontinue further study treatment and continue in the study for safety follow-up visits. The subject will be managed according to standard of care and the investigator's judgment based on the results of the histological diagnosis from the unscheduled biopsy. Additional instructions for collecting ectocervical biopsies are detailed in Appendix A. All biopsy samples/excised tissue will be sent to the central pathology lab for review by PAC.

Version Date: 01Jun2022

CONFIDENTIAL

Version 4.1

Page 59 of 87

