4.3.3. Per Protocol

The per-protocol (PP) population comprises subjects who receive all doses of Study Treatments and have no protocol violations and who have the analysis endpoint of interest. Subjects in this sample will be grouped to treatment arms as randomized. Analyses on the PP population will be considered supportive of the corresponding ITT population for the analysis of efficacy. Additional analyses on the PP population will utilize the Week 36 timeframe result regardless of any procedure performed before the Week 36 timeframe, thus serving as sensitivity analyses regarding early intervention. Subjects excluded from the PP population will be identified and documented prior to unblinding of the study database.

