Proportion of subjects with no evidence of squamous atypia, LSIL or HSIL on histology sample and no evidence of HPV-16 and/or HPV-18 by type specific HPV testing at Week 36 visit	Subject with no histologic evidence of cervical HSIL squamous atypia, or LSIL at Week 36 and no evidence of HPV-16 and/or HPV-18 at Week 36 AND Subject in which an excision or biopsy sample was NOT obtained between initial dose up to Week 36	Subject with histologic evidence of cervical HSIL, squamous atypia, or LSIL AIS, cervical carcinoma at Week 36 OR Subject with evidence of HPV-16 or HPV-18 at Week 36 OR Subject in which an excision or biopsy sample was obtained between initial dose up to Week 36 OR Subjects with no Week 36 sample result
Proportion of subjects with no progression of cervical HSIL to cervical carcinoma from baseline on histology sample at Week 36 visit	Subject with no histologic evidence of a worsening cervical condition at Week 36 relative to baseline AND Subject in which an excision or biopsy sample was NOT obtained between initial dose up to Week 36	Subject with histologic evidence of worsening of cervical condition at Week 36 relative to baseline OR Subject in which an excision or biopsy sample was obtained between initial dose up to Week 36 OR Subjects with no Week 36 sample result
Proportion of subjects who have cleared HPV-16 and/or HPV-18 on specimens from non-cervical anatomic locations (i.e., oropharynx, vagina and intra-anal) at Week 36 visit	Subject with no evidence of HPV-16 and/or HPV- 18 on specimens from non-cervical anatomic locations ^f at Week 36	Subject with evidence of HPV-16 or HPV-18 on specimens from non-cervical anatomic locations at Week 36 OR Subjects with no Week 36 sample result

Final Statistical Analysis Plan, Version 1.2 Date Issued: 310CT2022

a. No evidence of HSIL is defined by histology as negative, squamous atypia, or LSIL. The first tissue removal sample within the timeframe determines the histology endpoint.

b.The efficacy time frame is defined by those who have undergone a biopsy or surgical excision at any time starting from 14 days prior to the protocol-specified target date of Week 36

c. Excludes ECC-only samples

d. The most recent HPV clearance result prior to first tissue removal, which includes results from the same date, within the time frame determines the HPV clearance endpoint.

e. No evidence of squamous atypia, CIN1, CIN2 or CIN3 on biopsies or excisional treatment

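### The per-protocol sensitivity analysis of non-progression can score a carcinoma excised before the Week 36 window as non-progression, and the ITT version pools early biopsies and missing samples with true progression

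*SAP*

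**What the plan says.** SAP 8.1.2, Table 2, names the endpoint "Proportion of subjects with no progression of cervical HSIL to cervical carcinoma from baseline on histology sample at Week 36 visit". A woman is a non-responder on any one of three grounds:

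- "Subject with histologic evidence of worsening of cervical condition at Week 36 relative to baseline"
- "Subject in which an excision or biopsy sample was obtained between initial dose up to Week 36"
- "Subjects with no Week 36 sample result"

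Protocol 3.2.3, Table 7, has the same three grounds, including "Subjects with no Week 36 visit sample result". A footnote there exempts ECC-only samples from the early-tissue ground. In SAP Table 2 the matching footnote mark is attached only to the first row, not to the non-progression row. In both documents the first tissue removed inside the efficacy window decides the histology. SAP 8.1.1 opens that window at Day 238 for the primary endpoint.

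Protocol 3.1.4 and 6.4.14 give the reason for the early-tissue ground: "Removal of additional tissue by biopsy before Week 36 will bias results toward improvement regardless of whether the subject is in the active or placebo" arm. Protocol 6.4.15 adds that "All biopsy samples/excised tissue will be sent to the central pathology lab for review by PAC".

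Four analyses apply to this endpoint: ITT, mITT, per-protocol (PP), and a PP variant. On the variant, SAP 4.3.3 says "Additional analyses on the PP population will utilize the Week 36 timeframe result regardless of any procedure performed before the Week 36 timeframe". Protocol 8.5.2.1 applies the same variant to the secondary endpoints. Neither document makes an exception for a carcinoma found before the window.

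**The concern.** For regression and clearance, early tissue is a contaminant: removing the lesion can produce a good Week 36 result. For progression it is also evidence, because it is taken on suspicion of progression and read by the PAC. The rules for endpoint 7 never use that reading.

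Two things follow. The PP variant can report as free of progression a woman whose cancer was confirmed and removed during the trial. The ITT analysis gives one score to carcinoma, to an early biopsy that showed no worsening, and to a missing sample. A between-arm difference in drop-out or in investigators' use of biopsy would then be reported, with a confidence interval, as a difference in non-progression.

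**Working it through.** **1. Scoring four women under the four planned analyses.** The rules are those of SAP Table 2 and SAP 4.3.1 to 4.3.3. Women A and B are taken to have all three doses and no violation.

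| Woman | ITT | mITT | PP | PP variant |
|---|---|---|---|---|
| A: carcinoma excised after dose 3 and before Day 238; Week 36 tissue without worsening | non-responder | non-responder | non-responder | **responder** |
| B: early biopsy without worsening; Week 36 tissue without worsening | non-responder | non-responder | non-responder | responder |
| C: no early tissue; no Week 36 sample | non-responder | not in set | not in set | not in set |
| D: no early tissue; carcinoma in Week 36 tissue | non-responder | non-responder | non-responder | non-responder |

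A and B receive the same score in every column, so no planned version tells a confirmed early cancer from an early biopsy without worsening. The mITT set requires the endpoint to be present. On its natural reading it drops C, but it leaves A and B pooled.

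**2. Is A's path open?** Dose 3 is at Week 12 and the window opens two weeks before Week 36, which leaves 36 - 2 - 12 = 22 weeks. Colposcopy is scheduled at Weeks 15 and 28 in that interval. Protocol 6.4.14 allows a biopsy on suspicion of progression, so the biopsy is not in itself a violation. Protocol 6.4.15 lets the woman stay in follow-up. The path closes if she missed a dose, has another violation, or has no Week 36 tissue.

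**3. HPV-003 as an illustration.** Neither document gives an expected rate for endpoint 7. Protocol 3.5.1 gives confirmed micro-invasive cancer as 2/114 = 1.75% (printed as 1.8%) and 2/155 = 1.29% (printed as 1.3%); both reproduce. Placebo specimens are 155 - 114 = 41, with no cancer. The same section gives arms of 125 and 42, which sum to the 167 women dosed (Protocol 1.3.1). Suppose that women without specimens are the missing ones:

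- Missing: 125 - 114 = 11 and 42 - 41 = 1.
- Non-responders: (11 + 2)/125 = 10.4% and 1/42 = 2.4%.
- Non-progression: 112/125 = 89.6% against 41/42 = 97.6%, difference -8.0 points (Miettinen-Nurminen 95% CI -15.2 to 2.5).
- Part due to missing specimens: 11/125 - 1/42 = 8.8 - 2.4 = 6.4 of the 8.0 points.
- Women with specimens only: 112/114 against 41/41, difference -1.8 points (95% CI -6.2 to 6.9).

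**4. Share of ITT non-responders without documented worsening.** Let m be the fraction with no Week 36 sample or with early tissue without worsening, and w the rate of worsening among the rest. The share is m / (m + (1 - m)w). All values of m are assumptions; 10% is the discontinuation level at which Protocol 4.3 considers supplementing enrolment, not a forecast. For w, 1.8% is the HPV-003 carcinoma rate on VGX-3100. The 5% and 10% are assumed, because the rule counts any worsening and CIN2 to CIN3 might qualify.

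| m | w = 1.8% | w = 5% | w = 10% |
|---|---|---|---|
| 5% | 0.05/0.0671 = 75% | 0.05/0.0975 = 51% | 0.05/0.145 = 34% |
| 10% | 0.10/0.1162 = 86% | 0.10/0.145 = 69% | 0.10/0.19 = 53% |
| 15% | 0.15/0.1653 = 91% | 0.15/0.1925 = 78% | 0.15/0.235 = 64% |

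**5. Differential drop-out alone.** With 198 women at 2:1 (132 and 66), no worsening in either arm, and missing samples of 10% and 5%, the result is 119/132 = 90.2% against 63/66 = 95.5%. That is a difference of -5.3 points (95% CI -12.5 to 3.5) with no progression at all.

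**The case against.** The early-tissue rule can be defended for this endpoint too. Woman A shows why: early excision can make Week 36 tissue look clean, and failure scoring in the ITT analysis guards against that. Missing-as-failure is likewise a usual conservative convention, and mITT is the planned check on it. The endpoint is status at Week 36. One early punch biopsy of a suspect lesion does not establish that status, and the HPV-003 cancers were found in larger excision samples after an initial biopsy without invasive cancer. All of this stands. It supports keeping the conservative ITT rule; it does not support a PP variant that removes the guard and puts nothing in its place.

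Three stronger readings are tempting, and the documents do not support them.

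- *The endpoint mostly measures drop-out and biopsies.* No rate of missing samples or early biopsies is given, and the share in step 4 falls to 34% under some assumptions.
- *The trial loses true cancers.* Woman A is still a non-responder in ITT, mITT and the main PP analysis. Confirmed carcinoma is an SAE (Protocol 7.10), and the optional group-level summary covers progression to cervical cancer (Protocol 8.5.6, SAP 10).
- *HPV-003 shows a non-progression deficit on VGX-3100.* The timing of specimens and cancers is not stated, the reports span 88 weeks, and the interval includes zero.

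**Conclusion.** The point holds in two parts. First, on the written rules, the PP variant scores woman A as non-progression, which contradicts the named endpoint. This is a matter of logic and needs no assumed rate; how often it would happen is unknown. Second, the ITT analysis pools early tissue without carcinoma (ECC-only samples excepted) and missing samples with true progression. mITT deals with the missing samples but not with the early tissue.

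The size of the second part rests on assumed rates: 34% to 91% of non-responders without documented worsening for m of 5% to 15% and w of 1.8% to 10%. The HPV-003 counts (13/125 against 1/42, with 2 confirmed carcinomas) show the mechanism only.

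The consequence is limited. The endpoint is secondary and is reported without a p-value, and the primary conclusion is untouched.

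**What to change.** For endpoint 7 only, in Protocol Table 7 and SAP Table 2:

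1. State that PAC-confirmed carcinoma in any tissue taken after dose 1 through the Week 36 window counts as progression in every version, including the PP variant. Alternatively, exclude endpoint 7 from that variant.
2. Keep the conservative ITT rule if wanted, but report non-responders by arm in four groups: carcinoma, other worsening, early tissue without worsening, and no Week 36 sample.
3. Add a supportive sensitivity analysis on the worst PAC histology after dose 1.
4. Repeat the ECC-only footnote mark in the non-progression row of SAP Table 2.

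The cost is table wording and one extra display; the plan already sends all such tissue to the PAC, and no trial procedure changes. There are two small downsides. Endpoint 7 will treat early tissue differently from the regression endpoints. And because an early biopsy without carcinoma does not prove Week 36 status, the worst-histology version should stay supportive.

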 Among i) baseline biomarker-positive women and ii) all women, determine VGX-3100 efficacy compared to placebo as measured by histopathologic non-progression. 	 Proportion of women with no progression of cervical HSIL to cervical carcinoma from baseline on histology sample at Week 36 visit.
8. Among i) baseline biomarker-positive women and ii) all women, describe the clearance of HPV-16 and/or HPV-18 infection from non- cervical anatomic locations.	 Proportion of women who have cleared HPV-16 and/or HPV-18 on specimens from non-cervical anatomic locations (oropharynx,

CONFIDENTIAL

Version 4.1

Page 14 of 87

Secondary Objectives	Associated Secondary Endpoints
	vagina and intra-anal) at Week 36 Visit compared to baseline.
9. Among i) baseline biomarker-positive women and ii) all women, determine the humoral and cellular immune response of VGX-3100 compared with placebo at post dose 3 and Week 36 visit as assessed relative to baseline.	 9a. Levels of serum anti-HPV-16 and anti-HPV-18 antibody concentrations at Weeks 15 and 36 visits 9b. Interferon-γ ELISpot response magnitudes at baseline, Weeks 15 and 36 visits 9c. Flow Cytometry response magnitudes at baseline and Week 15 visits.
Exploratory Objectives	Associated Exploratory Endpoints

CONFIDENTIAL

Version 4.1

Page 15 of 87

Downloaded by

Study Design

Trial Treatment: 6 mg (1 ml) VGX-3100 Intramuscular injection followed by EP with the CELLECTRATM 5PSP device given at Day 0, Week 4 and Week 12

Efficacy Assessment: The primary endpoint for the Phase 3 study (HPV-303) is based upon the results of the Phase 2b study (HPV-003) and the Phase 3 study (HPV-301). Given that HPV persistence is an important factor in the clinical progression of cervical dysplasia and also based upon the findings of the secondary objective of the HPV-003 study, the responder definition for the HPV-303 primary endpoint determination will take into consideration both histological regression of cervical HSIL and clearance of high-risk HPV-16 and HPV-18.

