7.9 POST-STUDY REPORTING REQUIREMENTS

All AEs and SAEs including deaths, regardless of cause or relationship, must be reported for subjects on study (including any protocol-required post-treatment follow-up).

Investigators are not obligated to actively seek AEs or SAEs beyond the follow up period for subjects. However, if the investigator learns of an AE or SAE that occurs after the completion or termination visit

Version Date: 01Jun2022

CONFIDENTIAL

Version 4.1

Page 67 of 87

and the event is deemed by the investigator to be related to the study treatment, he/she should promptly document and report the event to the Sponsor.

7.10 EVENT REPORTING FOR DISEASE PROGRESSION OR EXCLUSIONARY HISTOLOGIC FINDINGS POST-STUDY TREATMENT

After starting study treatment, if there is histologic confirmation of progression of cervical HSIL to micro invasive or invasive squamous cell carcinoma, the event must be reported as an SAE. Post-study treatment histologic diagnosis of adenocarcinoma-in-situ or adenocarcinoma should also be reported as an SAE. In both instances, the condition for SAE reporting should be categorized as a medically important event unless another criterion is met.

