8.2 GENERAL CONSIDERATIONS

The statistical analysis of the data will be performed by Inovio Pharmaceuticals or its representative.

This is a two-arm, multi-center, placebo-controlled, blinded a' drandomized clinical trial in subjects with a histologic diagnosis of cervical HSIL. The study's primary endpoint is binary: regression to CIN1/normal and clearance of HPV-16 and/or HPV-18 infection, based on tissue collected at the Week 36 timeframe. The primary hypothesis is that VGX-3100 will be superior to placebo regarding the proportion who achieve the primary endpoint among baseline biomarker-positive women. Sc condary efficacy analyses involve regression to CIN1 and complete regression, cle .ance of HPV-16 and/or HPV-18 infection from cervical and non-cervical tissue, and non-progression of cervical lesions. Other secondary analyses concern safety, humoral and cellular immunological measures.

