- 2. Among all women, determine the efficacy of VGX-3100 compared to placebo with respect to combined histopathologic regression of cervical HSIL and virologic clearance of HPV-16 and/or HPV-18
- 3. Among i) baseline biomarker-positive women and ii) all women, determine VGX-3100 efficacy compared to placebo as measured by histopathologic regression of cervical HSIL.
- Among i) baseline biomarker-positive women and ii) all women, determine VGX-3100 efficacy compared to placebo as measured by virologic clearance of HPV-16 and/or HPV-18
- 5. Among i) baseline biomarker-positive women and ii) all women, determine VGX-3100 efficacy compared to placebo as measured by complete histopathologic regression of cervical HSIL to normal
- 6. Among i) baseline biomarker-positive women and ii) all women, determine VGX-3100 efficacy compared to placebo as measured by both complete histopathologic regression of cervical HSIL to normal and virologic clearance of HPV-16 and/or HPV-18
- 7. Among i) baseline biomarker-positive women and ii) all women, determine VGX-3100 efficacy compared to placebo as measured by histopathologic non-progression
- 8. Among i) baseline biomarker-positive women and ii) all women, describe the clearance of HPV-16 and/or HPV-18 infection from non-cervical anatomic locations
- 9. Among i) baseline biomarker-positive women and ii) all women, determine the humoral and cellular immune response following administration of VGX-3100 compared with placebo at post dose 3 and Week 36 visits as assessed relative to baseline

2.3.Exploratory Objective

Downloaded on 5/2/2024

3. Investigational Plan

3.1.Overall Study Design and Plan

HPV-303 is a prospective, randomized, double-blind, placebo controlled, multi-center study to determine the efficacy, safety, and tolerability of VGX-3100 administered by IM injection followed by EP delivered with CELLECTRA[™] 5PSP in adult women with histologically confirmed cervical HSIL (CIN2, CIN3) associated with HPV-16/18.

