8.1.2. Secondary Efficacy Endpoints

For the secondary efficacy endpoints listed in Section 3.2.2 of this SAP, the analysis method will be the same as for the primary endpoint described in Section 8.1.1, but without p-values.

In addition, the definition of responder and non-responder for each endpoint is defined in Table 2.

Final Statistical Analysis Plan, Version 1.2 Date Issued: 310CT2022

Table 2. Definition of Secondary Endpoints Responder and Non-Responder

Endpoint	Responder	Non-Responder				
Proportion of subjects with no evidence of cervical HSIL on	Subject with no histologic evidence of cervical HSIL ^a at Week 36 ^b	Subject with histologic evidence of cervical HSIL, AIS, cervical carcinoma at Week 36				
histology sample at Week 36 visit	AND	OR				
	Subject in which an excision or biopsy sample ^c was NOT obtained between initial dose up to	Subject in which an excision or biopsy sample was obtained between initial dose up to Week 36				
	Week 36	OR				
		Subjects with no Week 36 sample result				
Proportion of subjects with no evidence of HPV-16 and/or	Subject with no evidence of HPV-16 and/or HPV-18 ^d at Week 36	Subject with evidence of HPV-16 or HPV-18 at Week 36				
HPV-18 in cervical samples by type specific HPV testing at Week 36 visit	AND Subject in which an excision or biopsy sample was	Subject in which an excision or biopsy sample was obtained between initial dose up to Week 36				
	NOT obtained between initial dose up to Week 36	OR				
		Subjects with no Week 36 sample result				
Proportion of subjects with no evidence of squamous atypia,	Subject with no histologic evidence of cervical HSIL, squamous atypia, or LSIL ^e at Week 36	Subject with histologic evidence of cervical HSIL, squamous atypia, LSIL, AIS, cervical carcinoma at Week 36				
LSIL, or HSIL on histology sample at Week 36 visit	AND	OR				
	Subject in which an excision or biopsy sample was NOT obtained between initial dose up to Week 36	Subject in which an excision or biopsy sample was obtained between initial dose up to Week 36				
		OR				
		Subjects with no Week 36 sample result				

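### Secondary endpoint 7 is labelled as progression to cervical carcinoma, but its governing rule fails any histologic worsening, so the reported rate would include women without carcinoma

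*SAP*

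**What the plan says.** The label is the same wherever endpoint 7 is listed: the Protocol synopsis, the Protocol 3.2 table, SAP 3.2.2 item 7 and the endpoint column of SAP Table 2. The Protocol form is "Proportion of women with no progression of cervical HSIL to cervical carcinoma from baseline on histology sample at Week 36 visit".

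The scoring rule is in Protocol 3.2.3, Table 7, and in the same SAP Table 2 row. The SAP responder is a "Subject with no histologic evidence of a worsening cervical condition at Week 36 relative to baseline"; the Protocol non-responder text begins "Subject with histologic evidence of worsening of cervical" and goes on to the condition at Week 36 compared with baseline. SAP 8.1.2 makes the table govern: "the definition of responder and non-responder for each endpoint is defined in Table 2". The row also fails women with an interval excision or biopsy and women with no Week 36 result.

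Other text points both ways. Objective 7 in SAP 2.2 speaks of efficacy "compared to placebo as measured by histopathologic non-progression", and Protocol 8.2 lists "and non-progression of cervical lesions"; both fit the wider rule. Protocol 7.10 fits the narrower label: on "histologic confirmation of progression of cervical HSIL to micro invasive or invasive squamous cell carcinoma, the event must be reported as an SAE". It then treats AIS in a separate sentence. That section concerns SAE reporting and is not linked to the endpoint.

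**The concern.** Label and rule describe different events. A reader of the results table would take the endpoint 7 rate as the share of women who did not progress to carcinoma. The rule would have removed from that share women whose lesion rose in grade but stayed within HSIL, and most naturally women with AIS. A secondary efficacy result that looks like a cancer outcome would then be driven partly by something else.

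The timing also matters. Protocol 8.5.6 and SAP section 10 allow group-level unblinded summaries, including adverse events of progression to cervical cancer, once Week 36 data are complete. If label and rule are reconciled after that, the choice could follow the results.

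**Working it through.** The plan states no rate, sample size or power for endpoint 7, so there is no figure of its own to reproduce. The check is a comparison of readings, followed by two illustrations of size.

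**Step 1: score each Week 36 finding under label and rule.** Every woman enters with CIN2 or CIN3. Assume a Week 36 sample and no interval biopsy.

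| Baseline to Week 36 | Label (carcinoma only) | Governing rule (any worsening) |
|---|---|---|
| Same or lower grade | responder | responder |
| CIN2 to CIN3 | responder | non-responder |
| CIN2 or CIN3 to AIS | responder | most naturally non-responder; not named |
| CIN2 or CIN3 to carcinoma | non-responder | non-responder |

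- CIN2 to CIN3: SAP 4.2 calls CIN2 the milder disease and stratifies on CIN grade at screening, and SAP 4.3.1 refers to CIN grade at Week 36. Both ends of the comparison exist, and the change is a worsening.
- AIS: exclusion criterion 1 (Protocol synopsis and 4.2) bars AIS in any screening specimen, so AIS at Week 36 is new against recorded baseline histology. SAP Table 1, the other histology rows of SAP Table 2, and Protocol Tables 4, 5, 6 and 8 name AIS and carcinoma as failures. The non-progression row names neither.

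**Step 2: illustrate the placing of AIS with HPV-003 (Protocol 3.5.1).** Confirmed carcinoma: 2 VGX-3100, 0 placebo. Confirmed AIS: 1 and 1. Women with specimens: 114 VGX-3100 and, by subtraction, 155 − 114 = 41 placebo. Differences are failure rates, VGX-3100 minus placebo, with Miettinen-Nurminen 95% intervals.

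| Failures counted | VGX-3100 | Placebo | Difference (95% CI), points |
|---|---|---|---|
| Carcinoma, specimens only | 2/114 = 1.75% | 0/41 = 0% | 1.75 (−6.9 to 6.2) |
| Carcinoma + AIS, specimens only | 3/114 = 2.63% | 1/41 = 2.44% | 0.19 (−10.2 to 5.6) |
| Carcinoma, no specimen = failure | 13/125 = 10.40% | 1/42 = 2.38% | 8.02 (−2.5 to 15.2) |
| Carcinoma + AIS, no specimen = failure | 14/125 = 11.20% | 2/42 = 4.76% | 6.44 (−5.3 to 14.4) |

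The last two rows take arm sizes of 125 and 42 (the Week 62 cytology denominators in 3.5.1), so women without a specimen number 125 − 114 = 11 and 42 − 41 = 1. Counting AIS shifts the difference by 1.75 − 0.19 = 1.56 points, or 8.02 − 6.44 = 1.58 points.

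**Step 3: CIN2 to CIN3.** The documents give no frequency. The shift in the pooled failure rate is (CIN2 share) × (proportion of CIN2 women who reach CIN3). SAP 4.2 caps the share at 50%. Assuming, for scale only, a share of 25% to 50% and a proportion of 5% to 30%, the shift runs from 0.25 × 0.05 = 1.25 points to 0.50 × 0.30 = 15 points, or 2.5 to 29.7 of 198 women. For comparison, the HPV-003 carcinoma rate of 2/155 would give 198 × 2/155 = 2.6 women with carcinoma.

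**The case against.** The strongest reply is that the rule is clear and only the label is loose. SAP 8.1.2 says Table 2 defines the responder, the stated objective is non-progression without reference to carcinoma, and CIN2 to CIN3 is plainly a worsening. AIS was excluded at entry, so it is new at Week 36. On this view nobody following the table would score these women differently, and the remedy is a relabelling. Most of that stands, and it limits the point to the mismatch and the unnamed AIS category.

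It also rules out some stronger inferences:

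- A reader might infer that CIN2 to CIN3 can be scored either way, because SAP 8.1.1 defines HSIL as CIN2 and CIN3 together. That definition belongs to the primary endpoint; the non-progression row compares the cervical condition with baseline, not the HSIL tier.
- A reader might infer that AIS is fully open, because Protocol 3.5.1 says punch biopsy can miss it. That concerns when the lesion arose. The endpoint compares recorded histology, and carcinoma missed at screening would raise the same question without becoming ambiguous.
- A reader might infer that CIN2 to CIN3 is summarised nowhere else. The exploratory sections are removed from the public text, so this cannot be shown, and SAP 4.4 says all collected data will be listed.
- A reader might infer that carcinoma would be obscured. It would not: Protocol 7.10 makes carcinoma and AIS reportable as SAEs, and cancer progression is a named item in the optional group-level summary.

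What the reply does not remove is that the table's own row carries both the carcinoma label and the worsening rule, and no passage says which meaning the reported result has.

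**Conclusion.** The point holds as a label-against-rule contradiction, repeated in both documents and resolved in neither. Following the plan as written yields a carcinoma-labelled rate that fails women without carcinoma. It should be corrected, but its reach is small: one secondary estimate and interval, in biomarker-positive women and in all women, with no p-value.

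The 1.6-point AIS figure is an illustration only. It rests on one confirmed case per arm over 88 weeks, undated, with a derived placebo denominator, and the intervals overlap almost entirely. The 1.25 to 15 point range for CIN2 to CIN3 rests wholly on assumed inputs and is not an estimate.

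**What to change.** Before any group-level unblinded summary, make label and rule agree in both documents.

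The smaller change keeps the rule. Relabel endpoint 7 as histopathologic non-progression in the Protocol synopsis, Protocol 3.2, SAP 3.2.2 and the SAP Table 2 endpoint column, which matches the objective and Protocol 8.2. State in Protocol Table 7 and SAP Table 2 that CIN2 to CIN3, AIS and carcinoma count as worsening. Carcinoma confirmed by the Pathology Adjudication Committee can be reported beside it as a separate count.

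The alternative keeps the label. Restrict the histologic criterion in both tables to committee-confirmed carcinoma, state how AIS is classed, and align Protocol 8.2.

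Either way the cost is a few lines of wording. No new data are needed, because CIN grade is determined at screening and at Week 36, and the primary analysis does not change.
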